5.3.3 Assessment of Severity of Adverse Events

The adverse event severity grading scale for the NCI CTCAE (v5.0) will be used for assessing adverse event severity. [Table 2](#) will be used for assessing severity for adverse events that are not specifically listed in the NCI CTCAE.

Table 2 Adverse Event Severity Grading Scale for Events Not Specifically Listed in NCI CTCAE

| Grade | Severity |
|-------|--|
| 1 | Mild; asymptomatic or mild symptoms; clinical or diagnostic observations only; or intervention not indicated |
| 2 | Moderate; minimal, local, or non-invasive intervention indicated; or limiting age-appropriate instrumental activities of daily living ^a |
| 3 | Severe or medically significant, but not immediately life-threatening; hospitalization or prolongation of hospitalization indicated; disabling; or limiting self-care activities of daily living ^{b, c} |
| 4 | Life-threatening consequences or urgent intervention indicated ^d |
| 5 | Death related to adverse event ^d |

NCI CTCAE = National Cancer Institute Common Terminology Criteria for Adverse Events.

Note: Based on the most recent version of NCI CTCAE (v5.0), which can be found at:

http://ctep.cancer.gov/protocolDevelopment/electronic_applications/ctc.htm

- ^a Instrumental activities of daily living refer to preparing meals, shopping for groceries or clothes, using the telephone, managing money, etc.
- ^b Examples of self-care activities of daily living include bathing, dressing and undressing, feeding oneself, using the toilet, and taking medications, as performed by patients who are not bedridden.
- ^c If an event is assessed as a "significant medical event," it must be reported as a serious adverse event (see Section 5.4.2 for reporting instructions), per the definition of serious adverse event in Section 5.2.2.
- ^d Grade 4 and 5 events must be reported as serious adverse events (see Section 5.4.2 for reporting instructions), per the definition of serious adverse event in Section 5.2.2.

5.3.4 Assessment of Causality of Adverse Events

Investigators should use their knowledge of the patient, the circumstances surrounding the event, and an evaluation of any potential alternative causes to determine whether an adverse event is considered to be related to the study drug, indicating "yes" or "no" accordingly. The following guidance should be taken into consideration (see also Table 3):

- Temporal relationship of event onset to the initiation of study drug
- Course of the event, with special consideration of the effects of dose reduction, discontinuation of study drug, or reintroduction of study drug (as applicable)
- Known association of the event with the study drug or with similar treatments
- Known association of the event with the disease under study
- Presence of risk factors in the patient or use of concomitant medications known to increase the occurrence of the event
- Presence of non-treatment-related factors that are known to be associated with the occurrence of the event

Table 3 Causal Attribution Guidance

| | |
|---|--|
| Is the adverse event suspected to be caused by the study drug on the basis of facts, evidence, science-based rationales, and clinical judgment? | |
| YES | There is a plausible temporal relationship between the onset of the adverse event and administration of the study drug, and the adverse event cannot be readily explained by the patient's clinical state, intercurrent illness, or concomitant therapies; and/or the adverse event follows a known pattern of response to the study drug; and/or the adverse event abates or resolves upon discontinuation of the study drug or dose reduction and, if applicable, reappears upon re-challenge. |
| NO | An adverse event will be considered related, unless it fulfills the criteria specified below. Evidence exists that the adverse event has an etiology other than the study drug (e.g., preexisting medical condition, underlying disease, intercurrent illness, or concomitant medication); and/or the adverse event has no plausible temporal relationship to administration of the study drug (e.g., cancer diagnosed 2 days after first dose of study drug). |

For patients receiving combination therapy, causality will be assessed individually for each protocol-mandated therapy.

5.3.5 Procedures for Recording Adverse Events

Investigators should use correct medical terminology/concepts when recording adverse events on the Adverse Event eCRF. Avoid colloquialisms and abbreviations.

Only one adverse event term should be recorded in the event field on the Adverse Event eCRF.

5.3.5.1 Injection Reactions

Adverse events that occur during or within 24 hours after study drug administration should be captured as individual signs and symptoms on the Adverse Event eCRF rather than an overall diagnosis (e.g., record dyspnea and hypotension as separate events rather than a diagnosis of anaphylactic reaction).

5.3.5.2 Diagnosis versus Signs and Symptoms

A diagnosis (if known) should be recorded on the Adverse Event eCRF rather than individual signs and symptoms (e.g., record only liver failure or hepatitis rather than jaundice, asterixis, and elevated transaminases). However, if a constellation of signs and/or symptoms cannot be medically characterized as a single diagnosis or syndrome at the time of reporting, each individual event should be recorded on the Adverse Event eCRF. If a diagnosis is subsequently established, all previously reported adverse events based on signs and symptoms should be nullified and replaced by one adverse event report based on the single diagnosis, with a starting date that corresponds to the starting date of the first symptom of the eventual diagnosis.

5.3.5.3 Adverse Events That Are Secondary to Other Events

In general, adverse events that are secondary to other events (e.g., cascade events or clinical sequelae) should be identified by their primary cause, with the exception of severe or serious secondary events. A medically significant secondary adverse event that is separated in time from the initiating event should be recorded as an independent event on the Adverse Event eCRF. For example:

- If vomiting results in mild dehydration with no additional treatment in a healthy adult, only vomiting should be reported on the eCRF.
- If vomiting results in severe dehydration, both events should be reported separately on the eCRF.
- If a severe gastrointestinal hemorrhage leads to renal failure, both events should be reported separately on the eCRF.
- If dizziness leads to a fall and consequent fracture, all three events should be reported separately on the eCRF.
- If neutropenia is accompanied by an infection, both events should be reported separately on the eCRF.

All adverse events should be recorded separately on the Adverse Event eCRF if it is unclear as to whether the events are associated.

5.3.5.4 Persistent or Recurrent Adverse Events

A persistent adverse event is one that extends continuously, without resolution, between patient evaluation timepoints. Such events should only be recorded once on the Adverse Event eCRF. The initial severity (intensity or grade) of the event will be recorded at the time the event is first reported. If a persistent adverse event becomes more severe, the most extreme severity should also be recorded on the Adverse Event eCRF. Details regarding any increases or decreases in severity will be captured on the Adverse Event Intensity or Grade Changes eCRF. If the event becomes serious, it should be reported to the Sponsor immediately (i.e., no more than 24 hours after learning that the event became serious; see Section [5.4.2](#) for reporting instructions). The Adverse Event eCRF should be updated by changing the event from "non-serious" to "serious," providing the date that the event became serious, and completing all data fields related to serious adverse events.

A recurrent adverse event is one that resolves between patient evaluation timepoints and subsequently recurs. Each recurrence of an adverse event should be recorded as a separate event on the Adverse Event eCRF.

5.3.5.5 Abnormal Laboratory Values

Not every laboratory abnormality qualifies as an adverse event. A laboratory test result must be reported as an adverse event if it meets any of the following criteria:

- Is accompanied by clinical symptoms

- Results in a change in study treatment (e.g., dosage modification, treatment interruption, or treatment discontinuation)
- Results in a medical intervention (e.g., potassium supplementation for hypokalemia) or a change in concomitant therapy
- Is clinically significant in the investigator's judgment

Note: For oncology trials, certain abnormal values may not qualify as adverse events.

It is the investigator's responsibility to review all laboratory findings. Medical and scientific judgment should be exercised in deciding whether an isolated laboratory abnormality should be classified as an adverse event.

If a clinically significant laboratory abnormality is a sign of a disease or syndrome (e.g., alkaline phosphatase and bilirubin $5 \times$ ULN associated with cholestasis), only the diagnosis (i.e., cholestasis) should be recorded on the Adverse Event eCRF.

If a clinically significant laboratory abnormality is not a sign of a disease or syndrome, the abnormality itself should be recorded on the Adverse Event eCRF, along with a descriptor indicating whether the test result is above or below the normal range (e.g., "elevated potassium," as opposed to "abnormal potassium"). If the laboratory abnormality can be characterized by a precise clinical term per standard definitions, the clinical term should be recorded as the adverse event. For example, an elevated serum potassium level of 7.0 mEq/L should be recorded as "hyperkalemia."

Observations of the same clinically significant laboratory abnormality from visit to visit should only be recorded once on the Adverse Event eCRF (see Section [5.3.5.4](#) for details on recording persistent adverse events).

5.3.5.6 Abnormal Vital Sign Values

Not every vital sign abnormality qualifies as an adverse event. A vital sign result must be reported as an adverse event if it meets any of the following criteria:

- Is accompanied by clinical symptoms
- Results in a change in study treatment (e.g., dosage modification, treatment interruption, or treatment discontinuation)
- Results in a medical intervention or a change in concomitant therapy
- Is clinically significant in the investigator's judgment

It is the investigator's responsibility to review all vital sign findings. Medical and scientific judgment should be exercised in deciding whether an isolated vital sign abnormality should be classified as an adverse event.

If a clinically significant vital sign abnormality is a sign of a disease or syndrome (e.g., high blood pressure), only the diagnosis (i.e., hypertension) should be recorded on the Adverse Event eCRF.

Observations of the same clinically significant vital sign abnormality from visit to visit should only be recorded once on the Adverse Event eCRF (see Section 5.3.5.4 for details on recording persistent adverse events).

5.3.5.7 Abnormal Liver Function Tests

The finding of an elevated ALT or AST ($>3 \times \text{ULN}$) in combination with either an elevated total bilirubin ($>2 \times \text{ULN}$) or clinical jaundice in the absence of cholestasis or other causes of hyperbilirubinemia is considered to be an indicator of severe liver injury (as defined by Hy's Law). Therefore, investigators must report as an adverse event the occurrence of either of the following:

- Treatment-emergent ALT or AST $>3 \times \text{ULN}$ in combination with total bilirubin $>2 \times \text{ULN}$
- Treatment-emergent ALT or AST $>3 \times \text{ULN}$ in combination with clinical jaundice

The most appropriate diagnosis or (if a diagnosis cannot be established) the abnormal laboratory values should be recorded on the Adverse Event eCRF (see Section 5.3.5.2) and reported to the Sponsor immediately (i.e., no more than 24 hours after learning of the event), either as a serious adverse event or an adverse event of special interest (see Section 5.4.2).

5.3.5.8 Deaths

All deaths that occur during the protocol-specified adverse event reporting period (see Section 5.3.1), regardless of relationship to study drug, must be recorded on the Adverse Event eCRF and immediately reported to the Sponsor (see Section 5.4.2). This includes death attributed to progression of NASH.

Death should be considered an outcome and not a distinct event. The event or condition that caused or contributed to the fatal outcome should be recorded as the single medical concept on the Adverse Event eCRF. Generally, only one such event should be reported. If the cause of death is unknown and cannot be ascertained at the time of reporting, "unexplained death" should be recorded on the Adverse Event eCRF. If the cause of death later becomes available (e.g., after autopsy), "unexplained death" should be replaced by the established cause of death. The term "**sudden death**" should not be used unless combined with the presumed cause of death (e.g., "sudden cardiac death").

If the death is attributed solely to progression of NASH, "nonalcoholic steatohepatitis progression" should be recorded on the Adverse Event eCRF.

Deaths that occur after the adverse event reporting period should be reported as described in Section 5.6.

5.3.5.9 Preexisting Medical Conditions

A preexisting medical condition is one that is present at the screening visit for this study. Such conditions should be recorded on the General Medical History and Baseline Conditions eCRF.

A preexisting medical condition should be recorded as an adverse event only if the frequency, severity, or character of the condition worsens during the study. When recording such events on the Adverse Event eCRF, it is important to convey the concept that the preexisting condition has changed by including applicable descriptors (e.g., "more frequent headaches").

5.3.5.10 Lack of Efficacy or Worsening of NASH

Events that are clearly consistent with the expected pattern of progression of the underlying disease should not be recorded as adverse events. These data will be captured as efficacy assessment data only. In most cases, the expected pattern of progression will be based on histologic and imaging criteria. In rare cases, the determination of clinical progression will be based on symptomatic deterioration. However, every effort should be made to document progression through use of objective criteria. If there is any uncertainty as to whether an event is due to disease progression, it should be reported as an adverse event.

5.3.5.11 Hospitalization or Prolonged Hospitalization

Any adverse event that results in hospitalization (i.e., inpatient admission to a hospital) or prolonged hospitalization should be documented and reported as a serious adverse event (per the definition of serious adverse event in Section 5.2.2), except as outlined below.

An event that leads to hospitalization under the following circumstances should not be reported as an adverse event or a serious adverse event:

- Planned hospitalization required by the protocol
- Hospitalization for a preexisting condition, provided that all of the following criteria are met:

The hospitalization was planned prior to the study or was scheduled during the study when elective surgery became necessary because of the expected normal progression of the disease

The patient has not experienced an adverse event

An event that leads to hospitalization under the following circumstances is not considered to be a serious adverse event, but should be reported as an adverse event instead:

- Hospitalization that was necessary because of patient requirement for outpatient care outside of normal outpatient clinic operating hours

5.3.5.12 Cases of Accidental Overdose or Medication Error

Accidental overdose and medication error (hereafter collectively referred to as "special situations"), are defined as follows:

- Accidental overdose: accidental administration of a drug in a quantity that is higher than the assigned dose
- Medication error: accidental deviation in the administration of a drug

In some cases, a medication error may be intercepted prior to administration of the drug.

Special situations are not in themselves adverse events, but may result in adverse events. Each adverse event associated with a special situation should be recorded separately on the Adverse Event eCRF. If the associated adverse event fulfills seriousness criteria or qualifies as an adverse event of special interest, the event should be reported to the Sponsor immediately (i.e., no more than 24 hours after learning of the event; see Section 5.4.2). For BFKB8488A (or matching placebo), adverse events associated with special situations should be recorded as described below for each situation:

- Accidental overdose: Enter the adverse event term. Check the "Accidental overdose" and "Medication error" boxes.
- Medication error that does not qualify as an overdose: Enter the adverse event term. Check the "Medication error" box.
- Medication error that qualifies as an overdose: Enter the adverse event term. Check the "Accidental overdose" and "Medication error" boxes.

In addition, all special situations associated with BFKB8488A (or matching placebo), regardless of whether they result in an adverse event, should be recorded on the Adverse Event eCRF as described below:

- Accidental overdose: Enter the drug name and "accidental overdose" as the event term. Check the "Accidental overdose" and "Medication error" boxes.
- Medication error that does not qualify as an overdose: Enter the name of the drug administered and a description of the error (e.g., wrong dose administered, wrong dosing schedule, incorrect route of administration, wrong drug, expired drug administered) as the event term. Check the "Medication error" box.
- Medication error that qualifies as an overdose: Enter the drug name and "accidental overdose" as the event term. Check the "Accidental overdose" and "Medication error" boxes. Enter a description of the error in the additional case details.
- Intercepted medication error: Enter the drug name and "intercepted medication error" as the event term. Check the "Medication error" box. Enter a description of the error in the additional case details.

As an example, an accidental overdose that resulted in a headache would require two entries on the Adverse Event eCRF, one entry to report the accidental overdose and one entry to report the headache. The "Accidental overdose" and "Medication error" boxes would need to be checked for both entries.

5.3.5.13 Patient-Reported Outcome Data

Adverse event reports will not be derived from PRO data by the Sponsor, and safety analyses will not be performed using PRO data. Sites are not expected to review the PRO data for adverse events.

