4.5.14 Clinical Outcome Assessments

Patient-reported outcome (PRO) instruments will be completed to assess the treatment benefit and more fully characterize the safety profile of BFKB8488A. In addition, PRO instruments will enable the capture of each patient's direct experience with BFKB8488A.

PRO data will be collected through use of the following instruments: The Columbia-Suicide Severity Rating Scale (C-SSRS), the Patient Health Questionnaire-9 (PHQ-9), and the Appetite Sensations Visual Analogue Scale (VAS).

The C-SSRS is a tool used to assess the lifetime suicidality of a patient as well as any new instances of suicidality. The electronic self-rated version of the C-SSRS will be used to assess suicidal ideation and behavior (SIB) at baseline and monitor for changes in SIB at subsequent visits. For positive scores, the investigator will be alerted and should follow up with the patient to provide the appropriate intervention as soon as possible.

The PHQ-9 will be administered for monitoring of potential depression throughout the study. The PHQ-9 is a self-administered diagnostic instrument that scores each of the 9 Diagnostic and Statistical Manual of Mental Disorders criteria of depression. Following study of construct and criterion validity, the PHQ-9 has been shown as a reliable and valid measure of depression severity (Kroenke et al. 2001).

The Appetite Sensations VAS (see [Appendix 2](#)) consists of eight items with words anchored at each end expressing the most positive and the most negative rating of hunger, satiety, fullness, prospective food consumption, desire to eat something fatty, salty, sweet, or savory. This scale has reproducibility, power, and validity (Flint et al. 2000). The scales have been used with both immediate ("Right Now") and retrospective ("Past Week") recall periods (Womble et al. 2003) and have demonstrated sensitivity to effects of lorcaserin on prospective food consumption (Martin et al. 2011).

PRO instruments will be self-administered at the clinic at specified timepoints during the study [REDACTED]. [REDACTED],

[REDACTED], instruments will be administered before the patient receives any information on disease status, prior to the performance of non-PRO assessments, and prior to the administration of study treatment, unless otherwise specified.

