5.1.1.7 CNS Effects

[REDACTED] Additionally, to assess the potential CNS effects, mood, suicidal ideation and behavior will be assessed in the study for the duration of this trial by administration of the C-SSRS every 2 weeks. Prospective scales that monitor depression such as the PHQ-9 will also be administered periodically.

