5.1.2.8 CNS Effects and Mood

The effects on CNS and mood will be closely monitored. If a patient has a PHQ-9 score at or above 15 (moderately severe depression), at or above 10 (moderate depression) with a score of 2 or 3 for the question “Thoughts that you would be better off dead, or thoughts of hurting yourself in some way?”, or a C-SSRS suicidal ideation type 4 or 5 or behavior, he/she would be referred for timely psychiatric evaluation and/or discontinued from treatment. Study drug should be held while awaiting psychiatric evaluation. Additional monitoring of anxiety or insomnia may be performed if needed.

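### Section 5.3.5.13 bars all patient-reported data from safety analyses, which shuts out the C-SSRS and PHQ-9 scores that the protocol collects partly to characterise safety

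*Combined protocol and SAP*

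**What the plan says.** Section 4.5.14 (Clinical Outcome Assessments) defines which instruments count as patient-reported outcomes (PROs): "PRO data will be collected through use of the following instruments: The Columbia-Suicide Severity Rating Scale (C-SSRS), the Patient Health Questionnaire-9 (PHQ-9"), with the Appetite Sensations VAS as the third. It gives their purpose: PRO "instruments will be completed to assess the treatment benefit and more fully characterize the safety profile of BFKB8488A". The C-SSRS is to be used "to assess suicidal ideation and behavior (SIB) at baseline and monitor for changes in SIB at subsequent visits", and for sites it adds: "For positive scores, the investigator will be alerted and should follow up with the patient".

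Section 5.1.1.7 (CNS Effects) says that mood, suicidal ideation and behavior "will be assessed in the study for the duration of this trial by administration of the C-SSRS every 2 weeks", with the PHQ-9 given periodically.

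Section 5.1.2.8 (CNS Effects and Mood) calls for psychiatric referral and/or discontinuation in three cases: a PHQ-9 total of 15 or more; a total "at or above 10 (moderate depression) with a score of 2 or 3 for the question" on self-harm; or C-SSRS ideation of type 4 or 5, or behavior. Meanwhile, "Study drug should be held while awaiting psychiatric evaluation".

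Section 5.3.5.13 (Patient-Reported Outcome Data) says that the sponsor will not derive adverse event reports from PRO data, and continues: "safety analyses will not be performed using PRO data. Sites are not expected to review the PRO data for adverse events". It names no instrument and makes no exception.

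**The concern.** Data gathered partly to describe a drug's safety should be allowed into the safety analysis. Here one section gives the two scales that purpose and another removes every PRO from that analysis. The trial compares 50, 75 and 100 mg with placebo and treats CNS effects as a risk needing monitoring, so a by-dose view of mood and suicidality scores is a natural output. As the protocol stands, the by-dose safety comparison can use these scores only indirectly, where a finding becomes an adverse event or a reason for stopping treatment.

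There is also a practical question for sites. If they are not expected to review PRO data for adverse events, it is unclear how they are to notice a PHQ-9 score that obliges them to hold the drug.

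**Working it through.** No figure in the plan is at issue, so the check is a comparison of sections.

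**1. Analysis rule against purpose.** Section 5.3.5.13 excludes PRO data from safety analyses. Section 4.5.14 makes the C-SSRS and PHQ-9 PRO data and says PROs help characterise safety. Both statements cannot be followed in full. Sections 5.3.5.13, 6.5 and 6.9 show no redaction, and the sentences relied on in 4.5.14 are intact.

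**2. Analysis rule against monitoring and stopping rules.** Sections 5.1.1.7 and 4.6.1 concern monitoring and the management of individual patients; neither plans an analysis. The neighbouring section on safety biomarkers, 5.3.5.14, carries an extra sentence ruling out use of those data in managing patients. Section 5.3.5.13 has no such sentence, so PRO scores may still drive holds and stops. There is no contradiction here. Section 4.6.1 names neither scale: its ideation criterion is tied to the C-SSRS through 5.1.2.8, and the PHQ-9 is not among its criteria.

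**3. Site review.** For the C-SSRS, an alert on positive scores can coexist with no routine review for adverse events. For the PHQ-9, 5.1.2.8 requires action on the score, but the visible text describes no alert. A hold or discontinuation that follows is arguably an adverse event under 5.2.1, if the scale counts as a clinical test. Acting on the score and not reviewing it for adverse events are then hard to reconcile.

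**4. What triggers no hold or stopping rule.** The PHQ-9 rule in 5.1.2.8 is: act if total ≥ 15, or if total ≥ 10 and self-harm item ≥ 2.

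| PHQ-9 total | Item 0 or 1 | Item 2 or 3 |
|---|---|---|
| 15 or more | action | action |
| 10 to 14 | no action | action |
| below 10 | no action | no action |

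The protocol itself labels a score of 10 as moderate depression, so the 10 to 14 cell with no action is not trivial. For the C-SSRS, 5.1.2.8 acts on ideation types 4 and 5 and on behavior. Lower types lead only to the alert and follow-up in 4.5.14.

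**5. What still reaches the adverse event table.** Under 5.2.1 and 5.3.1, unfavorable symptoms are adverse events, and events noted by staff are recorded as well as those patients report. Threshold crossings that lead to a hold will often be recorded. Ideation below type 4 reaches the investigator through the alert and can be recorded too. What remains is the 10 to 14 cell, smaller PHQ-9 shifts, and C-SSRS ideation that nobody enters as an event.

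**6. Other planned routes.** The safety endpoints in 2.2 are adverse events, vital signs and laboratory results. Section 6.5 names no scale summary. The only PRO analysis planned is for the Appetite VAS (2.6 and 6.9). The ongoing remit of the Internal Monitoring Committee in 3.1.2 names adverse events and laboratory abnormalities, not PRO scores.

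**The case against.** The best defence is that 5.3.5.13 is a narrow rule about adverse event derivation and safety tables, and that the rest of the protocol deals with these scales properly. Much of that stands. The alert, hold, referral and discontinuation provisions are untouched. Section 6.5 is brief on all safety data and does not describe the vital-sign or laboratory summaries either, so its silence on the scales proves little. The DAP is not available and may say more. Section 5.3.5.13 would not forbid a descriptive table placed outside the safety analyses, and the monitoring committee reviews unblinded safety data and can ask for further analyses.

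The analysis conflict survives this. A DAP safety table of the scores would contradict the protocol, and moving the same table under another heading to avoid the rule would only show that the rule is mis-scoped.

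Three stronger readings are tempting, and the documents do not support them:

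- A reader might infer that sites are told to ignore suicidality scores, or that patients are unprotected. The text says only that review for adverse events is not expected, and the C-SSRS alert and the action rules remain in force.
- A reader might infer that 5.1.1.7 and 4.6.1 are also contradicted. They govern monitoring and patient management, which 5.3.5.13 does not restrict.
- A reader might count the scheduled questionnaires as a measure of the loss. That is a volume of data, and it may include a pre-dose baseline. It says nothing about signal.

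**Conclusion.** The concern holds, at minor severity. The unqualified bar in 5.3.5.13 defeats a purpose that 4.5.14 gives these scales. Followed as written, it keeps C-SSRS and PHQ-9 scores out of every by-arm safety summary. The no-review sentence is a real difficulty for the PHQ-9 only.

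The documents give no event rates or adverse event capture rates for these scales, so no size can be put on a missed effect and none is claimed.

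The conclusion rests on the protocol text as published. The DAP, the monitoring committee charter and the schedule of activities are not visible, and parts of 4.5.14 and 5.1.1.7 are redacted. A PHQ-9 alert described in any of these would ease the site-review point. It would not change the analysis point.

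**What to change.** In 5.3.5.13, exempt the C-SSRS and PHQ-9 from the no-safety-analysis wording, and exempt at least the PHQ-9 from the no-review wording. Leave both for the Appetite VAS.

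In 6.5, add descriptive by-arm summaries in the safety population, without tests:

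- patients with treatment-emergent C-SSRS ideation, by type, and with behavior;
- PHQ-9 change from baseline;
- patients crossing the PHQ-9 thresholds already set in 5.1.2.8.

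No new clinical action rule is needed. The cost is one wording change and three tables, with no added data collection, since under 7.3 the sponsor receives the PRO data in machine-readable form. The drawback is sparse tables. With about 20 patients at 50 mg, one patient is 1/20 = 5% of the arm, against 1/60 = 1.7% at 75 or 100 mg and 1/40 = 2.5% on the fixed-dose placebo. The tables should therefore be read as description.
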